### 9.3 Duration of Therapy

Study participation may conclude when any of the following events occur:

- Participant withdrawal
- At the discretion of the investigator
- Disease progression
- Intolerance of therapy or unacceptable toxicity

The reason for discontinuation and effective date should be documented. The PI should be promptly notified of the change in participant status.

### 9.4 Study Response Assessments

Safety assessment will occur through the study and consist of continuous surveillance and recording of adverse events (AEs) and serious adverse events (SAEs).

After the end of treatment, each subject will be followed for 30 days for adverse event monitoring (serious adverse events may be collected for 90 days after the end of treatment). Subjects may have post-treatment follow-up for disease status up to 5 years, or until disease progression, initiating a non-study cancer treatment, withdrawing consent, or becoming lost to follow-up.

4. Non-Hodgkin Lymphoma: PET-CT and CT (Diagnostic quality) after 2 cycles (8 weeks), then Diagnostic CT of chest, abdomen, and pelvis every 3 cycles (12 weeks) thereafter. Response assessment will be based on the Lugano Criteria
  - a. Initial response assessment after 2 cycles (8 weeks) with PET-CT and diagnostic CT
  - b. Diagnostic CT every 3 cycles thereafter
5. Chronic lymphocytic leukemia: PET-CT and CT (Diagnostic quality) after 2 cycles (8 weeks), then Diagnostic CT every 3 cycles (12 weeks) thereafter. A bone marrow aspirate +/- biopsy will be obtained at screening and to confirm CR. Response assessment based on IWCLL criteria
  - a. Initial response assessment after 2 cycles (8 weeks) with PET-CT and diagnostic CT
  - b. Diagnostic CT every 3 cycles (12 weeks) thereafter
6. Multiple myeloma: Assessment of serum protein electrophoresis (SPEP), serum free light chains (sFLC), every 4 weeks. 24-hour urine assessment of Bence-Jones Proteinuria only in subject who have this as sole marker of disease. Response assessment based on the IMWG. A bone marrow aspirate and biopsy will be obtained at screening and to confirm CR. PET-CT only to be performed for subjects with plasmacytoma as the only site of measurable disease at screening, after 2 cycles, then every 3 cycles (12 weeks) thereafter.

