### 9.1 Administration of Nivolumab

For treatment related questions, please contact [name] at [contact].

Nivolumab will be administered as a 30-minute IV infusion on Day 1 of each 28-day cycle.

The nivolumab dose is fixed at 480 mg. Doses of nivolumab may be interrupted, delayed, or discontinued depending on how well the participant tolerates the treatment. Refer to section 4.0 for further information on administration.

Management and dose delays associated with nivolumab AEs can be managed by referring to Section 4.8, or Section 9.5.

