|                                 | Grade 3 myocarditis   | Permanently discontinue |
|                                 | Requirement for 10 mg per day or greater prednisone or equivalent for more than 12 weeks  | Permanently discontinue |

|  |  |                          |
|--|--|--------------------------|
|  | Persistent Grade 2 or 3 adverse reactions lasting 12 weeks or longer | Permanently discontinued |
|--|--|--------------------------|

\* Resume treatment when adverse reaction improves to Grade 0 or 1.

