## 9.6 Subject Withdrawal/Discontinuation Criteria

Subjects may withdraw consent at any time for any reason or be dropped from the trial at the discretion of the investigator should any untoward effect occur. In addition, a subject may be withdrawn by the investigator for significant subject noncompliance with protocol requirements, or for administrative and/or other safety reasons. Subjects who require cessation of study therapy but do not withdraw consent may remain in standard follow-up for up to 5 years.

A subject must be discontinued from the trial for any of the following reasons:

- The subject or legal representative (such as a parent or legal guardian) withdraws consent.
- Confirmed radiographic disease progression
- Unacceptable adverse experiences
- Intercurrent illness that prevents further administration of treatment
- Investigator's decision to withdraw the subject
- The subject has a confirmed positive serum pregnancy test
- Noncompliance with trial treatment or procedure requirements
- The subject is lost to follow-up
- Administrative reasons

The End of Treatment and Follow-up visit procedures are listed in Appendix A (Study Calendar) and Section 11.1.5 (Visit Requirements). After the end of treatment, each subject will be followed for 30 days for adverse event and 90 days for serious adverse event monitoring. Subjects may have post-treatment follow-up up to 5 years per routine standard of care for survival and disease status.

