### 11.1.2.5 Tumor Imaging and Assessment of Disease

FDG-PET and diagnostic CT imaging will be required during study screening and 8 weeks after initiation of study drug for subjects with non-Hodgkin malignant lymphoma and CLL and FDG PET will be necessary for some subjects with multiple myeloma whose only disease is measured by that modality. Contrast-enhanced computed tomography (CT) of the chest, abdomen, and pelvis alone will be performed at each tumor assessment thereafter; neck CT is only necessary for those subjects with palpable neck lymphadenopathy. For measurement of response, 2014 criteria as described in “Recommendations for Initial Evaluation, Staging, and Response Assessment of Hodgkin and Non-Hodgkin Lymphoma: The Lugano Classification” will be used for NHL, and the IWCLL response criteria for CLL (see Appendix D & E).

All CT scans should be performed with IV contrast unless contraindicated, and abdominal and pelvis scans should be performed with oral contrast.

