Adverse events will be recorded from the time of a subject signing consent up until 30 days after the last dose of nivolumab, or 90 days after the last dose of nivolumab in the case of serious adverse events.

For subjects with multiple myeloma only.

The Sponsor-Investigator or sub-Investigator may waive screening bone marrow aspirate and biopsy requirements. For subjects with CLL/SLL and MM, repeat bone marrow biopsy only to be done after screening to confirm CR

Pregnancy test is only required in women of childbearing potential. Verbal report of pregnancy will be reported during conduct of the trial.

Tumor assessment imaging (see section 11.1.2.5) will be performed prior to cycle 3 (within 7 days of scheduled treatment dose) and every 3 cycles thereafter. Tumor assessment labs and/or imaging will also be performed as indicated per clinical standard of care (e.g. as appropriate for disease, to evaluate clinical suspicion of disease progression). Screening PET-CT and diagnostic CT done prior to screening up to day -42 may

be used for screening assessment. PET-CT and diagnostic CT will be performed at screening, then after 2 cycles on cycle 2 day 22. Thereafter, tumor assessment will comprise diagnostic CT of chest, abdomen, pelvis every 3 months. For multiple myeloma only, PET-CT should only be done amongst subjects in whom the only measurable disease is by imaging criteria – both at screening and for follow-up.

End of treatment evaluations should be done within 30 days (+/- 14 days) of the last dose of nivolumab or prior to the start of a new anti-cancer drug, whichever is first.

Correlative studies to include peripheral blood for storage for future biomarker analyses. Please see section 15 for details on blood collection and storage.

Long-term follow-up should be done according to the subject's physician standard of care. This may be performed at subjects' local physician's offices. Long-term follow-up will assess survival and disease progression. Subjects may be contacted by the study team until death, subject withdrawal of consent, lost to follow-up, or study termination, whichever occurs first.

If available, will be tested for PD-1 and PD-L1 IHC

The use of growth factors or transfusions to meet hematologic eligibility criteria is allowed

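### Disease assessments are timed both by treatment cycle and by calendar, with no rule for which governs when a dose is withheld, so progression can be recorded later in subjects with toxicity

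*Combined protocol and SAP*

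**What the plan says.** Dosing runs on a four-week cycle: "Nivolumab will be administered as a 30-minute IV infusion on Day 1 of each 28-day cycle" (Section 9.1). Disease assessment is timed in two ways.

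- **By cycle.** Section 10.3 puts the first on-study scan at cycle 2 day 22. Sections 10.4 and 10.5 list later CT under Day 1 visits at three-cycle intervals, with no week count. Footnote 5 to the Study Calendar says imaging "will be performed prior to cycle 3 (within 7 days of scheduled treatment dose) and every 3 cycles thereafter".
- **By calendar.** Section 11.1.2.5 says PET and CT are "required during study screening and 8 weeks after initiation of study drug". The same footnote 5 later says "tumor assessment will comprise diagnostic CT of chest, abdomen, pelvis every 3 months".
- **Both at once.** Section 9.4 and the synopsis give a cycle count with weeks in brackets, as in "Diagnostic CT every 3 cycles (12 weeks) thereafter".

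Myeloma serum markers are due every 4 weeks in Section 9.4, but Section 10 attaches them to Day 1 of each cycle.

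Table 2 (Section 9.5) withholds nivolumab for many Grade 2 or 3 reactions, with the instruction "Resume treatment when adverse reaction improves to Grade 0 or 1". Permanent discontinuation applies to "Persistent Grade 2 or 3 adverse reactions lasting 12 weeks or longer".

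After treatment, Section 9.6 says "Subjects may have post-treatment follow-up up to 5 years per routine standard of care for survival and disease status". In the calendar as it reads in the available text, the tumor assessment row is marked in the Post Therapy column. It has no mark under cycle 2 day 22 or in the long-term column, although footnote 7 says long-term follow-up assesses progression.

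**The concern.** Cycle counts and week counts are interchangeable only when every dose is given on time, and the plan expects that some will not be. Sites work from visit schedules. Section 10 and the calendar columns are laid out by cycle day, so the natural practice is to move the scan with the dose.

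The spacing of assessments would then depend on toxicity. Section 14.3 counts PFS to progression or death, and progression found on imaging is in practice dated at the scan that shows it. A stretched gap can therefore lengthen recorded PFS through the schedule and not through the drug. Duration of response also depends on scan dates. Two sites, or two subjects at one site, could follow different schedules and both comply with the protocol.

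**Working it through.** **The plan's own equivalences.** With a 28-day cycle, 3 × 28 / 7 = 12 weeks and 2 × 28 / 7 = 8 weeks. Both reproduce, but only with no delay. Three months is 3 × 365.25 / 12 = 91.3 days, or about 13 weeks.

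**First scan, no delay** (cycle 1 day 1 = Day 1):

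| Source | Rule | Study days |
|---|---|---|
| Section 10.3, calendar | Cycle 2 day 22 ± 3 | 28 + 22 = 50, so 47–53 |
| Footnote 5 | Within 7 days before cycle 3 (nominal Day 57) | 50–57 |
| Section 11.1.2.5 | 8 weeks from first dose | 57, no window given |

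These differ by a few days. The ± 3 days on the cycle 3 visit absorbs part of that: if cycle 3 is given on Day 54, Days 47–49 are within 7 days of it.

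**With one hold of h weeks, scans following cycles:**

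- later CT gap = 12 + h
- first scan, if the cycle 2 dose is the one held = 7 + h (cycle 2 day 22 is 49 / 7 = 7 weeks after first dose)
- myeloma marker gap = 4 + h

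| h (weeks) | Later CT gap | First scan (week) | Myeloma marker gap |
|---|---|---|---|
| 4 | 16 | 11 | 8 |
| 8 | 20 | 15 | 12 |
| 12 (limit) | 24 | 19 (Day 50 + 84 = 134) | 16 |

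Under the calendar reading the first scan stays at week 8 and later gaps stay at 12 to 13 weeks, whatever h is.

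**What this does to a recorded date.** Take scans at weeks 8, 20 and 32. A 4-week hold between the first two moves the later ones to 24 and 36. Progression at week 15 is recorded at week 24 instead of 20, which is 4 weeks late. Progression at week 22 is recorded at week 24 instead of 32, which is 8 weeks early. A progression inside the stretched gap is recorded late by up to the length of the hold. After that gap the schedule is only out of phase, and the error can go either way.

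**Average size, under assumptions that are not in the documents.** A sensitivity simulation used exponential progression times with medians of 8, 13 or 26 weeks. It gave 10%, 26% or 40% of subjects one hold of 4, 8 or 12 weeks, placed at random in one of the first three scan intervals. It included no clinically triggered scans and no deaths.

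- Mean delay in recorded progression, held subjects: 0.4 to 3.8 weeks. Subjects who progressed before their assigned hold count as zero.
- Mean delay over all subjects: 0.04 to 1.5 weeks.
- Median recorded time: unchanged with 13- or 26-week medians. With 8 weeks the median falls on a scan date, and the comparison is unstable.

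**How many subjects.** Section 4.9 cites Grade 3 or higher event rates of 19% (myeloma) to 26% (B-cell NHL) in an earlier nivolumab study. If these carried over, 0.19 × 20 = 3.8 to 0.26 × 20 = 5.2, or about 4 to 5 subjects. This is only a guide: not every such event leads to a hold, and Grade 2 holds would add to the count.

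**The case against.** Several arguments on the other side are sound.

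- **Imaging is not simply tied to cycles.** Section 11.1.2.5, part of footnote 5 and the bracketed weeks in Section 9.4 are calendar anchors, under which a hold moves nothing. This stands: the defect is an unresolved conflict, and the late scans are what follows if sites take the cycle reading.
- **A 24-week gap is a ceiling.** A reader might take the 12 weeks in Table 2 as the permitted dose delay. It limits how long a Grade 2 or 3 reaction may last. One reaction starts before the dose it holds, so a hold from that reaction alone falls short of 12 weeks, although separate reactions could add to it. Footnote 5 also provides for imaging on clinical suspicion of progression, which would shorten a gap.
- **Deaths are PFS events whatever the scan dates.** Most myeloma subjects are followed by serum markers. Both facts limit the effect, although the markers carry the same ambiguity.
- **Inflated duration of response is not established.** A gap after response lengthens it, but a gap before response delays the recorded onset and can shorten it.
- **Best overall response rate is not a time measure.** The first scan moves only under the cycle reading and only if the cycle 2 dose is late. A hold at cycle 3 leaves cycle 2 day 22 in place. A late first read can delay the 12-subject futility decision in Section 16.4, but delay alone does not bias the count. A subject who stopped for toxicity with no assessment at all would not be response evaluable under Section 16.1, but the Post Therapy tumor assessment makes that unlikely.
- **Subjects who stop for toxicity do not drop out of assessment.** A reader might infer this from Section 9.6 and the blank long-term cell. The Post Therapy mark, Section 9.4 and Section 11.1.5.3 all provide for disease follow-up. What is missing is a fixed interval.

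Nothing in the documents shows that subjects with toxicity are also the likelier responders. Nor is it fair to set a 24-week gap against the 5.1-month median survival in Section 3.1: that figure is for non-responders to CD19 CAR T-cells, and the same source gives 13.6 months for those who responded and later progressed.

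**Conclusion.** The concern holds as an unresolved conflict of anchors. The documents give cycle-based and calendar-based times for the same assessments, plan for dose holds that separate them, and do not say which prevails. Under the cycle reading, one hold of 4 to almost 12 weeks stretches a scan gap from 12 weeks to between 16 and nearly 24, and a held cycle 2 dose moves the first scan from about week 7 to as late as about week 19. The upper ends are near-worst cases that need one long hold and no clinically triggered scan.

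This can bias PFS upward and duration of response in either direction. The average shift is modest on the assumed inputs, and the effect on the primary endpoint is small. The documents do not support the stronger conclusions that PFS and duration of response are both inflated or that 24-week gaps are to be expected. The point is still worth correcting, because otherwise toxicity can determine when secondary endpoints are measured.

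**What to change.** State one anchor in the synopsis, Section 9.4, Sections 10.3 to 10.5, Section 11.1.2.5 and footnote 5. For example: *Disease assessments are scheduled in weeks from the first dose and are not moved when a dose is delayed. The first is at week 8, within one stated window. Later assessments are every 12 weeks, within a stated window. Myeloma serum markers are taken every 4 weeks on the same basis.* Remove cycle 2 day 22, the cycle counts and the three-month interval as competing anchors. Scans on clinical suspicion of progression stay as they are.

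Bring the calendar into line with the text: mark the first on-study scan, and mark disease status in the long-term column to match footnote 7, drawing on standard-of-care assessments. Fixed scan dates after treatment are not needed for this. They would replace the routine local follow-up of Section 11.1.5.3 with a new schedule of procedures.

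The cost is protocol wording. The planned scan frequency in calendar time is unchanged, and no dosing or withholding rule is touched. The downside is that some scans and blood draws will fall on non-dosing days.

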## 9.5 Nivolumab – Dosing Delays and Modifications

Adverse events (both non-serious and serious) associated with nivolumab exposure may represent an immunologic etiology. These adverse events may occur shortly after the first dose or several months after the last dose of treatment. The dose of nivolumab must be withheld for drug-related toxicities and severe or life-threatening AEs as per Table 5 below:

|                                 | Grade 3 myocarditis   | Permanently discontinue |
|                                 | Requirement for 10 mg per day or greater prednisone or equivalent for more than 12 weeks  | Permanently discontinue |

|  |  |                          |
|--|--|--------------------------|
|  | Persistent Grade 2 or 3 adverse reactions lasting 12 weeks or longer | Permanently discontinued |
|--|--|--------------------------|

\* Resume treatment when adverse reaction improves to Grade 0 or 1.

## 9.6 Subject Withdrawal/Discontinuation Criteria

Subjects may withdraw consent at any time for any reason or be dropped from the trial at the discretion of the investigator should any untoward effect occur. In addition, a subject may be withdrawn by the investigator for significant subject noncompliance with protocol requirements, or for administrative and/or other safety reasons. Subjects who require cessation of study therapy but do not withdraw consent may remain in standard follow-up for up to 5 years.

A subject must be discontinued from the trial for any of the following reasons:

- The subject or legal representative (such as a parent or legal guardian) withdraws consent.
- Confirmed radiographic disease progression
- Unacceptable adverse experiences
- Intercurrent illness that prevents further administration of treatment
- Investigator's decision to withdraw the subject
- The subject has a confirmed positive serum pregnancy test
- Noncompliance with trial treatment or procedure requirements
- The subject is lost to follow-up
- Administrative reasons

The End of Treatment and Follow-up visit procedures are listed in Appendix A (Study Calendar) and Section 11.1.5 (Visit Requirements). After the end of treatment, each subject will be followed for 30 days for adverse event and 90 days for serious adverse event monitoring. Subjects may have post-treatment follow-up up to 5 years per routine standard of care for survival and disease status.

## 10.0 CLINICAL AND LABORATORY EVALUATIONS

### 10.1 Schedule/Timing of Events (See Appendix A, Study Calendar)

#### 10.1.1 Screening Evaluations (Day -28 to Day -1)

- Research Consent, HIPAA
- Medical History, Including:
  - Hematologic, cytogenetic, flow cytometric, and histologic findings at time of diagnosis and at time of enrollment on the study
  - Prior therapies and response to therapies
- Physical Examination
- ECOG Performance Status (See Appendix B)

- Chemistries, Hematology
  - CBD (to include: white blood cell count, red blood cell count, hemoglobin, hematocrit, platelet count, absolute neutrophils, lymphocytes, monocytes, eosinophils, basophils, immature granulocytes)
  - Renal/Hepatic Function Panel (to include: sodium, potassium, chloride, total carbon dioxide, anion gap, glucose, urea nitrogen, creatinine, total protein, albumin, total bilirubin, direct bilirubin, calcium, phosphate, AST (GOT), Alkaline phosphatase, ALT (GPT), eGFR)
  - Magnesium, Lactate Dehydrogenase
- C-reactive Protein (CRP), Ferritin
- Uric Acid
- Serum or urine HCG within 14 days of cycle 1, day 1
- Coagulation Panel (To include INR, PT, PTT)
- Urinalysis
- T3, FT4, TSH
- Archival pre-treatment tumor biopsy (if available)
- Disease Specific:
  - Multiple Myeloma
    - Serum free light chain (SFLC) Assessment to include kappa to lambda ratio
    - SPEP with immunofixation
    - Bence Jones quantification, only in subjects for whom urinary Bence Jones quantitation represents best marker of disease
    - PET/CT (only amongst patients in whom plasmacytoma is the only measurable site of disease)
    - Bone marrow aspirate and biopsy, to include: histopathology, flow cytometry, FISH, and conventional cytogenetics
  - Non-Hodgkin Lymphoma, CLL
    - PET/CT and Diagnostic CT of the chest, abdomen, and pelvis. Diagnostic CT of neck only if palpable lymphadenopathy present
    - CLL Only: Bone marrow aspirate and biopsy, to include morphology, flow cytometry, FISH, cytogenetics

## 10.2 On Study Evaluations, Cycle 1

- Days 1
  - History and Physical Exam
  - Performance Status
  - Vital Signs (Including Temperature, Blood Pressure, Heart Rate, Oxygen Saturation)
  - Chemistry/Hematology
    - CBD
    - Renal/Hepatic Function Panel
    - Magnesium and LDH
  - CRP, Ferritin
  - Uric Acid

- Coagulation Panel
- T3, FT4, TSH
- Research Samples
  - Blood
    - Cytokines
    - Exploratory laboratory specimen
- Disease Specific:
  - Multiple Myeloma
    - SFLC, SPEP with immunofixation, Bence Jones Proteinuria (only if needed)
- Days 8, 15, 22
  - Chemistry/Hematology
    - CBD
    - Renal/Hepatic Function Panel
    - Magnesium and LDH
  - CRP, Ferritin
  - Uric Acid
  - Coagulation Panel
  - Research Samples
    - Blood
      - Cytokines
      - Exploratory laboratory specimen
- If subjects become febrile or develop symptoms of cytokine release syndrome, or tumor lysis during cycle 1, we may measure serum ferritin, CRP, coagulation panel, and tumor lysis markers at different time points outside those specified in the protocol, at discretion of the PI or treating provider.

### 10.3 On Study Evaluations, Cycle 2

- Day 1
  - History and Physical Exam
  - Performance Status
  - Vital Signs (Including Temperature, Blood Pressure, Heart Rate, Oxygen Saturation)
  - Chemistry/Hematology
    - CBD
    - Renal/Hepatic Function Panel
    - Magnesium and LDH
  - CRP, Ferritin
  - Uric Acid
  - Coagulation Panel
  - Research Samples
    - Blood
      - Cytokines
      - Exploratory laboratory specimen

- Disease Specific
  - Multiple Myeloma
    - SFLC, SPEP with immunofixation, Bence Jones Proteinuria (only if needed)
- Day 22 +/- 3 days
  - PET/CT and Diagnostic Quality CT of chest, abdomen, pelvis (Lymphoma)
  - PET/CT (Myeloma, only if measurable disease consists solely of plasmacytoma)

